11.1 Ixazomib³⁶

11.1.1 Other Names

Ixazomib is also referred to as [MLN9708](#) or [MLN2238](#).

11.1.2 Classification

Ixazomib is an oral proteasome inhibitor.

11.1.3 Storage and Stability

Upon receipt at the investigative site, ixazomib should remain in the blister and carton provided until use or until drug is dispensed. The container should be stored at the investigative site; do not store above 86°F (30°C); do not freeze. Ensure that the drug is used before the retest expiry date provided. Expiry extensions will be communicated accordingly with updated documentation to support the extended shelf life.

Ixazomib capsules dispensed to the patient for take-home dosing should remain in the blister packaging and refrigerated as noted above until the point of use. The investigative site is responsible for providing the medication to the patient in the correct daily dose configurations. Comprehensive instructions should be provided to the patient in order to ensure compliance with dosing procedures. Patients who are receiving take-home medication should be given only 1 cycle of medication at a time (starting with Cycle 7, may receive 3 cycles at a time). Patients should be instructed not to store the medication above 86°F (30°C); do not freeze for the duration of each cycle. Patients should be instructed to return their empty blister packs to the investigative site, rather than discarding them. Reconciliation will occur accordingly when the patient returns for their next cycle of take-home medication. Any extreme in temperature should be reported as an excursion and should be dealt with on a case-by-case basis.

Because ixazomib is an investigational agent, it should be handled with due care. Patients should be instructed not to chew, break, or open capsules. In case of contact with broken capsules, raising dust should be avoided during the clean-up operation. The product may be harmful by inhalation, ingestion, or skin absorption. Gloves and protective clothing should be worn during cleanup and return of broken capsules and powder to minimize skin contact.

The area should be ventilated and the site washed with soap and water after material pick-up is complete. The material should be disposed of as hazardous medical waste in compliance with federal, state, and local regulations.

In case of contact with the powder (e.g., from a broken capsule), skin should be washed immediately with soap and copious amounts of water for at least 15 minutes. In case of contact with the eyes, copious amounts of water should be used to flush the eyes for at least 15 minutes. Medical personnel should be notified. Patients are to be instructed on proper storage, accountability, and administration of ixazomib, including that ixazomib is to be taken as intact capsules.

11.1.4 Dose Specifics

Ixazomib is dispensed in a 4-week supply (starting with Cycle 7, may be dispensed in 12-week supply). The capsules will be individually packaged using cold-form foil-foil blisters that are in child-resistant carton. There will be 3 capsules in each wallet/carton. Patients will take one capsule on days 1, 8, and 15 of each cycle.

Refer to Section 6.5.1 and Table 6-3, Table 6-4 and Table 6-5 for Dose Delays and Modifications details.

11.1.5 Route of Administration

Ixazomib will be administered orally. Patients should be instructed to swallow ixazomib capsules whole, with water, and not to break, chew, or open the capsules. Ixazomib should be taken on an empty stomach (no food or drink) at least 1 hour before or at least 2 hours after food. Each capsule should be swallowed separately with a sip of water. A total of approximately 8 ounces (240 mL) of water should be taken with the capsules.

Missed doses can be taken as soon as the patient remembers if the next scheduled dose is 72 hours or more away for all cycles aside from Cycle 1 of the phase 1 portion of the study. Patients with dose delays in Cycle 1 shall be managed as described in Section 6.2. A double dose should not be taken to make up for a missed dose. If the patient vomits after taking a dose, the patient should not repeat the dose but should resume dosing at the time of the next scheduled dose.

Ixazomib Medication Diary will be reviewed for compliance and collected every cycle for Cycle 1-Cycle 6 (Appendix III). Starting with Cycle 7, Ixazomib Medication Diary will be reviewed and collected every 3 cycles.

11.1.6 Drug Interactions

Avoid concomitant administration of ixazomib with strong CYP3A inducers (such as rifampin, phenytoin, carbamazepine, and St. John's Wort).

11.1.7 Agent Availability

Ixazomib capsules will be supplied by Takeda Pharmaceuticals.

The ixazomib drug product is provided in strengths of 4.0-, 3.0-, and 2.3-mg capsules as the active boronic acid. The different dose strengths are differentiated by both capsule size and color as described below:

Dose Strength	Capsule Size	Capsule Color
4.0 mg	Size 4	Ivory
3.0 mg	Size 3	Light gray
2.3 mg	Size 2	Light pink

The initial supply of ixazomib will be sent directly to the site upon site activation. As needed, ixazomib may be requested by the principal investigator (or their authorized designees) at each participating institution. The investigator, or a responsible party designated by the investigator, must maintain a careful record of the receipt, disposition, and return/destruction (site's drug destruction policy must be reviewed and approved by PrECOG before any study drug can be destroyed at a site) of ixazomib.

11.1.8 Agent Ordering

PrECOG will be responsible for ordering drug for re-supply to the site. Requests for shipments of ixazomib will be coordinated between PrECOG and Takeda.

11.1.9 Agent Accountability

Ixazomib will be stored in a secure location. Only authorized pharmacy and study staff will have access to this agent. Drug accountability will be performed by PrECOG.

11.1.10 Side Effects

Adverse drug reactions such as thrombocytopenia, diarrhea, fatigue, nausea, vomiting, and rash have been associated with ixazomib treatment. Management guidelines regarding these events are outlined below. Further details of management of ixazomib AEs are described in the ixazomib IB.

11.1.10.1 Prophylaxis Against Risk of Reactivation of Herpes Infection

Patients may be at an increased risk of infection including reactivation of herpes zoster and herpes simplex viruses. Antiviral therapy such as acyclovir, valacyclovir, or other antivirals may be initiated as clinically indicated.

11.1.10.2 Nausea and/or Vomiting

Standard anti-emetics including 5-hydroxytryptamine 3 serotonin receptor antagonists are recommended for emesis if it occurs once treatment is initiated; prophylactic anti-emetics may also be considered at the physician's discretion. Dexamethasone should not be administered as an anti-emetic. Fluid deficit should be corrected before initiation of study drug and during treatment.

11.1.10.3 Diarrhea

Prophylactic antidiarrheals will not be used in this protocol. However, diarrhea should be managed according to clinical practice, including the administration of antidiarrheals once infectious causes are excluded. Fluid intake should be maintained to avoid dehydration. Fluid deficit should be corrected before initiation of treatment and during treatment.

11.1.10.4 Erythematous Rash With or Without Pruritus

As with bortezomib, rash with or without pruritus has been reported with ixazomib, primarily at the higher doses tested and when given with agents where rash is an overlapping toxicity. The rash may range from limited erythematous areas, macular and/or small papular bumps that may or may not be pruritic over a few areas of the body, to a more generalized eruption that is predominately on the trunk or extremities. Rash has been most commonly characterized as maculopapular or macular. To date, when it does occur, rash is most commonly reported within the first 3 cycles of therapy. The rash is often transient, self-limiting, and is typically Grade 1 to 2 in severity.

Symptomatic measures such as antihistamines or corticosteroids (oral or topical) have been successfully used to manage rash and have been used prophylactically in subsequent cycles. The use of a topical, IV, or oral steroid (e.g., prednisone \leq 10 mg per day or equivalent) is permitted. Management of a Grade 3 rash may require intravenous antihistamines or corticosteroids. Administration of ixazomib (and/or other causative agent if given in combination) should be modified per protocol and re-initiated at a reduced level from where rash was noted (Table 6-4).

In line with clinical practice, dermatology consult and biopsy of Grade 3 or higher rash or any SAE involving rash is recommended. Prophylactic measures should also be considered if a patient has previously developed a rash (e.g., using a thick, alcohol-free emollient cream on dry areas of the body or oral or topical antihistamines). Rare risks are Stevens-Johnson Syndrome, a severe and potentially life-threatening rash with skin peeling and mouth sores, toxic epidermal necrolysis (TEN) and drug

reaction with eosinophilia and systemic symptoms (DRESS syndrome) which should be managed symptomatically according to standard medical practice. Punch biopsies for histopathological analysis are encouraged at the discretion of the investigator.

11.1.10.5 Thrombocytopenia

Blood counts should be monitored regularly as outlined in the protocol with additional testing obtained according to standard clinical practice. Thrombocytopenia may be severe but has been manageable with platelet transfusions according to standard clinical practice. Ixazomib administration should be modified as noted as per dose modification recommendations in the protocol when thrombocytopenia occurs (Table 6-3). Therapy can be reinitiated at a reduced level upon recovery of platelet counts. A rare risk is thrombotic thrombocytopenic purpura (TTP), a rare blood disorder where blood clots form in small blood vessels throughout the body characterized by thrombocytopenia, petechiae, fever, or possibly more serious signs and symptoms. TTP should be managed symptomatically according to standard medical practice.

11.1.10.6 Neutropenia

Blood counts should be monitored regularly as outlined in the protocol with additional testing obtained according to standard clinical practice. Neutropenia may be severe but has been manageable. Growth factor support is not required but may be considered according to standard clinical practice. Ixazomib administration should be modified as noted as per dose modification recommendations in the protocol when neutropenia occurs (Table 6-3). Therapy can be reinitiated at a reduced level upon recovery of ANC s.

11.1.10.7 Fluid Deficit

Dehydration should be avoided since ixazomib may cause vomiting, diarrhea, and dehydration. Acute renal failure has been reported in patients treated with ixazomib, commonly in the setting of the previously noted gastrointestinal toxicities and dehydration.

Fluid deficit should be corrected before initiation of study drug and as needed during treatment to avoid dehydration.

11.1.10.8 Hypotension

Symptomatic hypotension and orthostatic hypotension with or without syncope have been reported with ixazomib. Blood pressure should be closely monitored while the patient is on study treatment and fluid deficit should be corrected as needed, especially in the setting of concomitant symptoms such as nausea, vomiting, diarrhea, or anorexia. Patients taking medications and/or diuretics to manage their blood pressure (for either hypo- or hypertension) should be managed according to standard clinical practice, including considerations for dose adjustments of their concomitant medications during the course of the trial. Fluid deficit should be corrected before initiation of study drug and as needed during treatment to avoid dehydration.

11.1.10.9 Posterior Reversible Encephalopathy Syndrome

One case of posterior reversible encephalopathy syndrome, which ultimately resolved, has been reported with ixazomib. This condition is characterized by headache, seizures and visual loss, as well as abrupt

increase in blood pressure. Diagnosis may be confirmed by magnetic resonance imaging (MRI). If the syndrome is diagnosed or suspected, symptom-directed treatment should be maintained until the condition is reversed by control of hypertension or other instigating factors.

11.1.10.10 Transverse Myelitis

Transverse myelitis has also been reported with ixazomib. It is not known if ixazomib causes transverse myelitis; however, because it happened to a patient receiving ixazomib, the possibility that ixazomib may have contributed to transverse myelitis cannot be excluded.

11.2 Ibrutinib³⁷

11.2.1 Other Names

Additional names for ibrutinib include Imbruvica® and PCI-32765.

11.2.2 Classification

Ibrutinib is an oral inhibitor of Bruton's tyrosine kinase. **Ibrutinib is approved for the treatment of patients with Mantle Cell Lymphoma and will be obtained commercially.**

11.2.3 Mode of Action

Ibrutinib is a small-molecule inhibitor of BTK. Ibrutinib forms a covalent bond with cysteine residue in the BTK active site, leading to inhibition of BTK enzymatic activity. BTK is a signaling molecule of the B-cell antigen receptor (BCR) and cytokine receptor pathways. BTK's role in signaling through the B-cell surface receptors results in activation of pathways necessary for B-cell trafficking, chemotaxis, and adhesion. Nonclinical studies show that ibrutinib inhibits malignant B-cell proliferation and survival in vivo as well as cell migration and substrate adhesion in vitro.

11.2.4 Storage and Stability

Ibrutinib is provided as white opaque 140 mg capsules marked with "ibr 140 mg" in black ink. Bottles should be stored at room temperature 20°-25°C (68°-77°F). Excursions are permitted between 15°C and 30°C (59°F to 86°F).

11.2.5 Dose Specifics

Ibrutinib shall be obtained through available commercial pharmacies. Patients should take the dose as prescribed by the treating investigator, with a maximum dose of 560 mg (4 tablets). Doses should be taken at the same time each day. Ibrutinib should be swallowed whole with water and the tablets should not be opened, broken, or chewed. If a dose of ibrutinib is not taken at the scheduled time, it can be taken as soon as possible on the same day with a return to the normal schedule the following day. Extra capsules of ibrutinib should not be taken to make up for the missed dose.

Refer to Section 6.5.2 and Table 6-6 for Dose Delays and Modifications details.

11.2.6 Route of Administration

Ibrutinib shall be consumed orally, with the full capsules swallowed for each dosing. Ibrutinib Medication Diary will be reviewed for compliance and collected every cycle for Cycle 1-6 [Appendix IV]. Starting with Cycle 7, Ibrutinib Medication Diary will be reviewed and collected every 3 cycles.

11.2.7 Drug Interactions

Ibrutinib is primarily metabolized by cytochrome P450 enzyme 3A.

11.2.7.1 CYP3A Inhibitors

Concomitant use of strong CYP3A inhibitors which would be taken chronically (e.g., ritonavir, indinavir, nefinavir, saquinavir, boceprevir, telaprevir, nefazodone) is not recommended. For short-term use (treatment for 7 days or less) of strong CYP3A inhibitors (e.g., antifungals and antibiotics such as ketoconazole, itraconazole, voriconazole, posaconazole, clarithromycin, telithromycin) consider interrupting ibrutinib until the CYP3A inhibitor is no longer needed. Reduce ibrutinib to 140 mg if a moderate CYP3A inhibitor must be used (e.g., fluconazole, darunavir, erythromycin, diltiazem, atazanavir, aprepitant, amprenavir, fosamprenavir, crizotinib, imatinib, verapamil, and ciprofloxacin).

Patients taking concomitant strong or moderate CYP3A4 inhibitors should be monitored more closely for signs of ibrutinib toxicity.

Avoid grapefruit and Seville oranges during ibrutinib treatment, as these contain moderate inhibitors of CYP3A.

11.2.7.2 CYP3A Inducers

Administration of ibrutinib with rifampin, a strong CYP3A inducer, decreased ibrutinib C_{max} and AUC by approximately 13- and 10-fold, respectively.

Avoid concomitant use of strong CYP3A inducers (e.g., carbamazepine, rifampin, phenytoin and St. John's Wort). Consider alternative agents with less CYP3A induction.

11.2.8 Availability

Ibrutinib shall be obtained through commercial or other sources and shall not be provided by the study.

11.2.9 Side Effects

There are no listed contra-indications for ibrutinib.

11.2.9.1 Hemorrhage

Fatal bleeding events have occurred in patients treated with ibrutinib. Grade 3 or higher bleeding events (subdural hematoma, gastrointestinal bleeding, hematuria and post procedural hemorrhage) have occurred in up to 6% of patients. Bleeding events of any grade, including bruising and petechiae, occurred in approximately half of patients treated with ibrutinib.

The mechanism for the bleeding events is not well understood.

Ibrutinib may increase the risk of hemorrhage in patients receiving antiplatelet or anticoagulant therapies.

Consider the benefit-risk of withholding ibrutinib for at least 3 to 7 days pre and post-surgery depending upon the type of surgery and the risk of bleeding.

11.2.9.2 Infections

Fatal and non-fatal infections have occurred with ibrutinib therapy. Grade 3 or greater infections occurred in 14% to 26% of patients. Cases of progressive multifocal leukoencephalopathy (PML) have occurred in patients treated with ibrutinib. Monitor patients for fever and infections and evaluate promptly.

11.2.9.3 Cytopenias

Treatment-emergent Grade 3 or 4 cytopenias including neutropenia (range, 19 to 29%), thrombocytopenia (range, 5 to 17%), and anemia (range, 0 to 9%) occurred in patients treated with ibrutinib.

11.2.9.4 Atrial Fibrillation

Atrial fibrillation and atrial flutter (range, 6 to 9%) have occurred in patients treated with ibrutinib, particularly in patients with cardiac risk factors, acute infections, and a previous history of atrial fibrillation. Periodically monitor patients clinically for atrial fibrillation. Patients who develop arrhythmic symptoms (e.g., palpitations, lightheadedness) or new onset dyspnea should have an ECG performed. If atrial fibrillation persists, consider the risks and benefits of ibrutinib treatment and dose modification.

11.2.9.5 Second Primary Malignancies

Other malignancies (range, 5 to 14%) including non-skin carcinomas (range, 1 to 3%) have occurred in patients treated with ibrutinib. The most frequent second primary malignancy was non-melanoma skin cancer (range, 4 to 11 %).

11.2.9.6 Tumor Lysis Syndrome

Tumor lysis syndrome has been reported with ibrutinib therapy. Monitor patients closely and take appropriate precautions in patients at risk for tumor lysis syndrome (e.g. high tumor burden).

11.2.10 Nursing/Patient Implications

Based on findings in animals, ibrutinib can cause fetal harm when administered to a pregnant woman. Ibrutinib caused malformations in rats at exposures 14 times those reported in patients with MCL and 20 times those reported in patients with Chronic Lymphocytic Leukemia or Waldenström's Macroglobulinemia, receiving the ibrutinib dose of 560 mg per day and 420 mg per day, respectively. Reduced fetal weights were observed at lower exposures. Advise women to avoid becoming pregnant while taking ibrutinib. If this drug is used during pregnancy or if the patient becomes pregnant while taking this drug, the patient should be apprised of the potential hazard to a fetus.

Women who are nursing are not eligible for this study and any woman who becomes pregnant over the course of the study will be removed from study therapy.

Ibrutinib is a Pregnancy Category D drug.

Please refer to the commercial package insert for full prescribing information.

12. Statistical Considerations

12.1.1 Phase I

For the phase I portion of the study, the primary objective will be to evaluate safety and toxicity of ixazomib when administered in combination with ibrutinib for patients with relapsed/refractory MCL, which we will assess by determining the MTD/RP2D as described in Section 6.2.1. We will determine this using a standard 3+3 design. The first cohort of 3 patients will be accrued to Dose Level 1 and will start therapy with ixazomib and ibrutinib. These 3 patients will be evaluated for a DLT during the first 28-day cycle, with DLT defined according to Table 6-2. If zero patients experience a DLT, the next cohort of 3 will be accrued at the next dose level. If 1 patient experiences a DLT, the next cohort of 3 will be accrued at the same dose level to further evaluate safety. If 2 or 3 patients experience a DLT, that level will be deemed too toxic and next cohort of 3 will be accrued to Dose Level (-1). If Dose Level (-1) proves too toxic, the study will end. If 1 or fewer out of 6 patients experience a DLT, then that level will be deemed the RP2D and the phase I trial will end.

Dose Level	Ixazomib	ibrutinib
	Days 1, 8, 15 of a 28 Day Cycle	Days 1-28 of a 28 Day Cycle
-1	3 mg	420 mg
1 Starting Dose	3 mg	560 mg
2	4 mg	560 mg

The table below summarizes the probabilities of dose escalation and de-escalation for a range of true DLT rates for the combination treatment using the standard 3+3 design.

	True DLT Rate							
	1%	5%	10%	15%	20%	30%	40%	50%
Probability of Dose escalation	.999	.973	.906	.814	.709	.494	.309	.172
Probability of Dose de-escalation	.001	.027	.094	.186	.291	.506	.691	.828

12.1.2 Phase II

For the phase II portion of the study, we will accrue patients to two cohorts (BTK-naïve [Cohort A] and BTK-pretreated [Cohort B]) simultaneously. The primary endpoint for the phase II study will be the CR rate, with planned comparison to historical controls. The target CR rate for the BTK-naïve cohort will be 40%, based on a historical rate of 21% for single agent ibrutinib, and the target CR rate for the BTK-pretreated cohort will be 23% based on a single agent CR rate of 8% for bortezomib. As a result, we will accrue 31 eligible, treated patients to each cohort for a total of 62 eligible, treated patients for the phase II study. To assure an adequate number of eligible, treated patients, up to 36 patients will be enrolled to each arm.

12.1.2.1 Administrative Changes: August 7, 2020

Due to administrative and/or industry sponsor reasons, it was decided that enrollment to Cohort B (BTK-pretreated cohort) will be stopped. The total number of BTK-pretreated patients enrolled was 2 as of August 7, 2020.

Enrollment to Cohort A (BTK-naïve cohort) will continue however, and up to the full accrual of 36 patients as initially planned. To supplement the enrollment of 36 patients in Cohort A, the BTK-naïve patients that were treated at the R2PD in Phase I (n=6) will contribute to the 36 patients needed for full accrual in Phase II.

The statistical operating characteristics, and primary endpoint, of the BTK-naïve cohort remains the same as indicated in Section 12.1.2 above.

12.2 Phase II

12.2.1 Primary Objectives

Patients will receive oral ixazomib and ibrutinib, in combination, at the RP2D. The efficacy of ixazomib and ibrutinib therapy will be assessed using CR rate. The CR rate will be the defined as the percentage of patients who achieve a CR (confirmed by BM biopsy) within the first 12 months of initiating treatment. Patients who are unevaluable or whose CR is not confirmed by BM biopsy will be included in the denominator as non-responders when computing the CR rate. Relapse/progression will be defined as either frank progression by clinical or laboratory exam (i.e., increased circulating monoclonal lymphocytes) or progressive disease by restaging CT, defined according to standard criteria.³⁴ Patients with isolated lymphocytosis shall not constitute progression in the absence of other findings.

In order to facilitate rapid accrual and to determine evidence of efficacy in multiple clinical settings, patients in the phase II portion of the study will be divided into two cohorts. Cohort A will include BTK-naïve patients. Cohort B will include BTK-pretreated patients. **August 7, 2020: BTK-pretreated cohort closed.**

Based on a historical single-agent 21% CR rate of ibrutinib in relapsed/refractory MCL⁴, we would consider a CR rate of 40% for the combination therapy in the BTK-naïve cohort (Cohort A) to be of interest. To detect an improvement of CR rate to 40% from the historical CR rate of 21%, a total of 31 patients will be accrued to Cohort A. This design will have 86% power and 10% one-sided Type I error using an exact binomial test and the null hypothesis will be rejected if CR is observed in 10 or more patients.

For the BTK-pretreated cohort (Cohort B) a CR rate of 23% will be of interest and a CR rate of 8%, based on a previously reported single agent CR rate for bortezomib, will not be of interest. To detect an improvement in CR rate to 23% from 8%, a total of 31 patients will also be accrued to Cohort B. This design will have 87% power and

10% one-sided Type I error using an exact binomial test and the null hypothesis will be rejected if CR is observed in 5 or more patients. **August 7, 2020: BTK-pretreated cohort closed.**

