8.5 Procedures in Case of Pregnancy

Prior to study enrollment, women of childbearing potential (WOCBP) and male patients with a female partner of childbearing potential must be advised of the importance of avoiding pregnancy during trial participation and the potential risk factors for an unintentional pregnancy, documented in the informed consent. In addition, all WOCBP should be instructed to contact the Investigator immediately if they suspect they might be pregnant (e.g., missed or late menstrual period) at any time during study participation.

Pregnancy of a female patient or the female partner of a male patient occurring while the patient is receiving study drug or within 3 months after the patient's last dose of study drug will be reported to PrECOG on a Pregnancy Form within 24 hours of the investigator's knowledge of the pregnancy.

All reports of congenital abnormalities/birth defects and spontaneous miscarriages should also be reported and handled as SAEs. Elective abortions without complications should not be handled as AEs.

The outcome of all pregnancies (spontaneous miscarriage, elective termination, normal birth including health of the newborn or congenital abnormality) must be followed and documented on the Pregnancy Form even if the subject was discontinued from the study treatment. Should pregnancy occur during a subject's participation, the subject will immediately be discontinued from the treatment and followed per protocol.

The study-specific Pregnancy Form can be found in the Study Reference Manual.

9. Measurement of Effect

LUGANO Classification

All disease response evaluation shall occur according to the Lugano classification³⁵.

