9.1 Scheduled Restaging Studies

All patients shall complete a PET/CT at the time of study enrollment. Thereafter, restaging shall include CT chest/abdomen/pelvis after cycles 3, 6, 9, and 12, and then every 6 months while on study therapy. PET/CT or MRI may be substituted for CT at the discretion of the treating investigator, especially in cases where lesions are not readily noted on CT. Patients who discontinue study therapy for reasons other than disease progression shall have CT's performed every 6 months until progression and/or initiation of a new therapy.

All patients with suspected CR based on routine restaging should have a PET/CT performed to confirm CR.

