9.2 Complete Response (CR)

In order to satisfy the criteria for a complete response, patients who undergo CT scan only must meet the following criteria:

- Target nodes/nodal masses must regress to ≤ 1.5 cm in longest transverse diameter.
- No extralymphatic sites of disease.
- Absent non-measured lesions.
- All organ enlargement must be regressed to normal.
- No new lesions.
- Bone marrow must be normal by morphology (must be evaluated at the time of suspected CR in patients with a positive bone marrow at enrollment).

Patients undergoing a PET/CT must meet the following criteria:

- Deauville score of 1, 2 or 3 on the 5-point scale.
- No new lesions.
- No evidence of FDG avid disease in the bone marrow.

NOTE: ALL PATIENTS WITH SUSPECTED CR WHO HAD BONE MARROW INVOLVEMENT AT SCREENING MUST UNDERGO A BONE MARROW BIOPSY TO CONFIRM RESPONSE.

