* **Scheduled Visits:** +/-3 day window is allowed for scheduled ixazomib therapy, required tests and/or visits except as otherwise noted. Delay due to holidays, weekends, bad weather or other unforeseen circumstances will be permitted.

1 Record date of diagnosis and stage.

2 CBC with differential and platelet count which includes WBC, ANC, Platelets, Hemoglobin, and Hematocrit required as noted below.

Phase I: Days 1, 8, 15 and 22 of Cycle 1; Days 1 and 15 of Cycle 2 and Cycle 3 (patients with ANC <1000 and/or platelets <100,000/mm³ on Day 15 should have blood counts done on Day 22 for Cycle 2 and 3 only); and Day 1 of subsequent cycles. **Phase I completed November 25, 2019.**

Phase II: Days 1 and 15 of Cycle 1 for which a clinic visit is required. Patients will be required to be seen in clinic on Day 1 of Cycles 2-7, then every 3 cycles thereafter. Labs are only required on the days patients are seen in clinic.

Results known prior to treatment administration. Patients experiencing cytopenias should have additional labs drawn as clinically indicated at the discretion of the treating physician.

3 Albumin, BUN/creatinine, uric acid, sodium, potassium, chloride, glucose, calcium, alkaline phosphatase, AST, ALT, total bilirubin, and total protein. Days 1 and 15 of Cycle 1 for which a clinic visit is required. Patients will be required to be seen in clinic on Day 1 of Cycles 2-7, then every 3 cycles thereafter. Labs are only required on the days patients are seen in clinic.

NOTE: Patients with a history of hepatitis B or C must have a negative peripheral blood Polymerase Chain Reaction (PCR) and may not be positive for Hepatitis B surface antigen.

- 4 25(OH) Vitamin D level.
- 5 Required for sexually active females of child-bearing potential.
- 6 PET/CT may be substituted for CT Chest/Abdomen/Pelvis at the discretion of the investigator.
- 7 Bone Marrow Biopsy to include: Aspirate and core biopsy morphologic evaluation and flow cytometry. Bone marrow biopsy will be repeated at the time of suspected CR for patients with involvement at the time of enrollment. Optional bone marrow biopsies and aspirates will be performed as clinically indicated at the end of therapy and/or time of progression.

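### Section 12.2.1 scores every CR without marrow-biopsy confirmation as a non-response, but Section 9.2 and footnote 7 ask for that biopsy only in patients with marrow involvement at entry

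*Protocol*

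**What the plan says.** Section 12.2.1 defines the primary CR rate as the "percentage of patients who achieve a CR (confirmed by BM biopsy) within the first 12 months of initiating treatment". It then adds a scoring rule: patients who are unevaluable, or "whose CR is not confirmed by BM biopsy will be included in the denominator as non-responders". Neither statement is limited to a subgroup, and neither refers back to Section 9.

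Section 9 sets the response criteria: "All disease response evaluation shall occur according to the Lugano classification". Among the CT criteria for CR in Section 9.2, normal marrow morphology "must be evaluated at the time of suspected CR in patients with a positive bone marrow at enrollment". The note closing that section has the same limit: "ALL PATIENTS WITH SUSPECTED CR WHO HAD BONE MARROW INVOLVEMENT AT SCREENING MUST UNDERGO A BONE MARROW BIOPSY TO CONFIRM RESPONSE". Footnote 7 to the Section 10 schedule agrees: "Bone marrow biopsy will be repeated at the time of suspected CR for patients with involvement at the time of enrollment". The confirmation step that applies to all patients is imaging, in Section 9.1: "All patients with suspected CR based on routine restaging should have a PET/CT performed to confirm CR".

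The design hypotheses are stated as CR rates with no mention of biopsy. Section 12.1.2 says: "The target CR rate for the BTK-naïve cohort will be 40%, based on a historical rate of 21% for single agent ibrutinib".

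**The concern.** The sentence in 12.2.1 sets the numerator of the primary endpoint, and the trial succeeds or fails on a fixed count of 10 or more CRs among 31 patients. Consider a patient whose marrow was negative at screening, who meets all the Section 9.2 criteria and whose PET/CT confirms the response. The protocol asks for no marrow biopsy at that point, so normally none exists. Section 9 calls this patient a complete responder and 12.2.1 calls the same patient a non-responder.

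If 12.2.1 is followed as written, valid CRs are discarded and the counted rate falls below the rate on which the power was calculated. Whether a marrow-negative CR counts would then depend on a biopsy that happened to be done for other reasons. If 12.2.1 is not followed as written, the analyst must choose between two definitions of the primary endpoint. In an open, single-arm trial that choice could be made with the responses already known.

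**Working it through.** **1. The passages side by side**

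| Place | Who needs a marrow biopsy at suspected CR | Marrow-negative patient, all Section 9 criteria met, no biopsy at CR |
|---|---|---|
| 9.2 criteria and note | Patients with marrow involvement at entry | CR |
| Section 10, footnote 7 | Patients with marrow involvement at entry | No biopsy scheduled |
| 9.1 | Not addressed; PET/CT confirms CR in all patients | Confirmed by PET/CT |
| 12.2.1 | No limit stated | Non-responder |

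The last row conflicts with the other three, and no passage expressly reconciles them.

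**2. The plan's own figures**

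Inputs from 12.2.1: n = 31, null rate 0.21, target rate 0.40, reject at 10 or more CRs, exact binomial test, stated power 86% and one-sided type I error 10%.

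- Type I error = P(X ≥ 10 | n = 31, p = 0.21) = 0.0975. A cutoff of 9 would give 0.187, so 10 is the smallest cutoff that stays under 10%.
- Power = P(X ≥ 10 | n = 31, p = 0.40) = 0.8566.

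The stated design reproduces, provided every CR that meets Section 9 is counted.

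**3. Effect of literal scoring**

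Let f be the share of true CRs that occur in marrow-negative patients with no biopsy at CR. The protocol gives no rate of marrow involvement, so f is an assumption and a range is shown. The same f is used under the null and the target rate.

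- Scored CR rate = p × (1 − f)
- Expected scored CRs = 31 × 0.40 × (1 − f)
- Power = P(X ≥ 10 | 31, 0.40 × (1 − f))
- Type I error = P(X ≥ 10 | 31, 0.21 × (1 − f))

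| f | Scored rate if the true rate is 40% | Expected scored CRs | Power | Type I error |
|---|---|---|---|---|
| 0 | 0.40 | 12.4 | 85.7% | 9.8% |
| 5% | 0.38 | 11.8 | 79.9% | 7.4% |
| 10% | 0.36 | 11.2 | 72.9% | 5.4% |
| 20% | 0.32 | 9.9 | 55.5% | 2.6% |
| 30% | 0.28 | 8.7 | 36.2% | 1.1% |
| 40% | 0.24 | 7.4 | 19.0% | 0.4% |

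Solving for f, power reaches 80% at f = 4.9% and 50% at f = 22.9%. At f = 20% the expected number of scored CRs (31 × 0.32 = 9.92) is already below the cutoff of 10, although the regimen meets its 40% target.

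**The case against.** The strongest reply is that the authors meant biopsy confirmation where Section 9.2 requires it. Section 9.2 is the only place where the CR criteria are set out, 12.2.1 uses the term without redefining those criteria, and the note in 9.2 ties the confirmatory biopsy to patients with an involved marrow. A marrow aspirate and biopsy is scheduled for every patient at screening, so a marrow-negative patient already has a marrow result on file. On that reading nothing is lost and the 86% and 10% stand. This is probably the intent, but it has to be inferred. Section 12.2.1 imposes the biopsy condition twice, the second time as an explicit non-responder rule, and a biopsy taken before treatment does not naturally confirm a later response.

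Two further points stand as limits. The power figures are a sensitivity table: they hold only under literal scoring and depend on an f that the protocol does not give. And the protocol does not show how marrow was handled in the study behind the 21% benchmark, so one cannot say from this document that the literal rule is stricter than the benchmark's rule.

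Leaving the matter to the statistical analysis plan does not answer the point. The protocol is not silent here: it states a rule that conflicts with its own response criteria and schedule.

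**Conclusion.** The point holds. As written, 12.2.1 turns a CR that satisfies Section 9 into a non-response whenever the patient had a negative marrow at entry and no biopsy at CR. That contradiction does not depend on any assumed figure.

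Only its size does. Given literal scoring and a true CR rate of 40%, power falls below 80% once f exceeds 4.9% and below 50% once f exceeds 22.9%. Type I error falls with it, so the risk is that an active regimen is missed, not that an inactive one is passed. The stated sample size, cutoff and power are correct in themselves. Because the sentence fixes the primary numerator, it must be corrected before the primary analysis, and preferably before responses are tabulated.

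**What to change.** Amend 12.2.1 so that the biopsy condition matches 9.2 and footnote 7. Suggested wording: *CR is determined per Sections 9.1 and 9.2. Bone marrow biopsy confirmation is required for scoring only in patients with marrow involvement at enrolment; such a patient with suspected CR and no confirmatory biopsy is counted as a non-responder.* Leave the 12-month window and the rule that unevaluable patients are non-responders as they are.

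Citing 9.1 alongside 9.2 makes clear that PET/CT confirmation still applies, since 9.2 on its own also lists a CT-only set of criteria. As an optional refinement, add a clause on how to score a patient whose screening marrow is missing or indeterminate.

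The cost is a one-sentence change. It affects scoring only and adds no biopsies, scans or patients. The sample size, cutoff and stated operating characteristics stay the same.
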